
Efficacy periods:

The start of the efficacy period for each individual starts on the date of first emicizumab treatment. The end of the efficacy period is defined as the date of the clinical cutoff or the date of withdrawal from/completion of the treatment whichever is earlier.

For patients who withdraw from the study before reaching the Week 1 visit, the duration of efficacy period is set to 1 day, and it starts and ends on the day of enrollment.

For patients whose dose is up-titrated, the efficacy period ends one day prior to the first day on the up-titrated dose (Efficacy period 1).

For patients whose dose is up-titrated, the bleeds occurring during the administration of the up-titrated dose are analyzed separately. The efficacy period on the up-titrated dose starts with the first day on this dose and ends on the day of the clinical cutoff or the date of withdrawal from/completion of treatment (Efficacy period 2).

For statistical evaluations (e.g. descriptive summaries) of post-baseline data summarized by visit, only measurements at scheduled visits are considered. If a measurement is repeated at a scheduled visit (or time point), then only the latest retest result will be used in calculation of the statistical summary. All data – including unscheduled measurements – will be included in the listings.

If a time interval was calculated in minutes, hours or days and needs to be converted into months or years the following conversion factors will be used:

1 year = 365.25 days

1 month = 30.4375 days

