#### **4.6.1.1 Bleeds**

The primary analysis will be based on treated bleeds (see definition 2.2.2.2). The number of bleeds over time will be estimated using a negative binomial (NB) regression model, which accounts for different follow-up times. The time that each patient stays in the study (efficacy period) will be included as an offset in the model.

An additional model which adjusts for number of bleeds (< 9 or ≥ 9, according to eCRF) in the last 24 weeks prior to study entry will be used to support the primary analysis.

In the rare case that the negative binomial model does not converge or no bleeds were observed for a given endpoint, the primary analysis will be based on “calculated” annualized bleed rate (ABR).

The ABR is calculated using the following formula (called Calculated ABR on all outputs):

$$\frac{\text{Number of bleeds during the efficacy period}}{\text{Number of days during efficacy period}} \times 365.25$$

The efficacy analyses will include the following endpoints defined in section 2.2.2: treated bleeds, all bleeds, treated joint bleeds, treated target joint bleeds and treated spontaneous bleeds. For each endpoint, the model based ABR will be estimated along with its corresponding 95% CI. In addition, the mean, 95% CI based on Exact Poisson, median, IQR, min and max will be provided for the calculated ABR.

A corresponding listing will be provided which will include for each patient the duration of efficacy period, number of bleeds together with calculated ABR for treated bleeds, all bleeds, treated spontaneous bleeds, treated joint bleeds and treated target joint bleeds (based on data before up-titration only). A separate listing will also be provided for the up-titrated population, based on data on or after the up-titration.

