#### **4.6.1.2 Number of Bleeds/ABR categories**

Number of patients with 0, 1-3, 4-10, >10 bleeds as well as number of patients with calculated ABR <1, 1-3.4, 3.5-10, >10 will be summarized. Figures including 95% CI will also be provided. All summaries and figures will be produced for treated bleeds, all bleeds and treated spontaneous bleeds.

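### The calculated-ABR categories in SAP 4.6.1.2 assign no category to values between 3.4 and 3.5, and closing the gap by rounding would shift the <1 category as well

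*SAP*

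**What the plan says.** SAP 4.6.1.2 plans a table of bleed-count categories and a table of ABR categories. For the second, the "number of patients with calculated ABR <1, 1-3.4, 3.5-10, >10 will be summarized". Figures with 95% CIs accompany the tables, and all are produced for treated bleeds, all bleeds and treated spontaneous bleeds.

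The variable being classified is defined in SAP 4.6.1.1: "The ABR is calculated using the following formula (called Calculated ABR on all outputs"). Its numerator is "Number of bleeds during the efficacy period", its denominator is "Number of days during efficacy period", and the ratio is multiplied by 365.25. I found no statement in the SAP that ABR is rounded before it is classified, or to how many decimals.

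The length of the denominator comes from SAP 4.1. On the start: "The start of the efficacy period for each individual starts on the date of first emicizumab treatment". It ends at the clinical cutoff or "the date of withdrawal from/completion of the treatment whichever is earlier". For an up-titrated patient the main efficacy period stops the day before the higher dose. The same section sets "1 year = 365.25 days" and "1 month = 30.4375 days".

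**The concern.** The limits 3.4 and 3.5 would be adjacent if the variable came in steps of 0.1. It does not: it is a whole number divided by a day count. Anything strictly between the two limits is left out of the table as specified, so the four percentages can fall short of 100%.

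The gap is easy to reach. Seven bleeds in exactly two years is an ABR of 3.5, so a patient with seven bleeds who is followed slightly longer drops straight into it.

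A programmer who meets an unclassified patient has to do something, and the SAP does not say what. Two natural repairs, moving the cut to 3.5 or rounding to one decimal, give different tables. In an open-label single-arm study that choice is better made in the SAP than after the data are seen.

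**Working it through.** The SAP states no computed figure for these categories, so there is nothing to reproduce first.

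**Inputs.** Formula and factor 365.25: SAP 4.6.1.1. Categories: SAP 4.6.1.2. Two years = 2 × 365.25 = 730.5 days, and 24 × 30.4375 = 730.5: SAP 4.1.

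**Step 1: which patients fall in the gap.** ABR = bleeds / days × 365.25, evaluated at whole days.

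| Bleeds | Days | ABR | Category as written |
|---|---|---|---|
| 7 | 730 | 3.5024 | 3.5-10 |
| 7 | 731 | 3.4976 | none |
| 7 | 751 | 3.4045 | none |
| 7 | 752 | 3.3999 | 1-3.4 |
| 6 | 627 to 644 | 3.4952 to 3.4030 | none |
| 5 | 522 to 537 | 3.4986 to 3.4008 | none |

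Seven bleeds is unclassified on 21 consecutive day values, 731 to 751. Patients with shorter follow-up reach the gap with fewer bleeds, as the last two rows show.

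**Step 2: what rounding to one decimal would do.** It splits the seven-bleed patients: 731 to 741 days becomes 3.5 (category 3.5-10), and 742 to 751 days becomes 3.4 (category 1-3.4). It also acts at the lower limit:

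- 2 × 365.25 / 731 = 0.9993, which is <1 unrounded and 1.0 rounded.
- 2 × 365.25 / 768 = 0.9512, which is <1 unrounded and 1.0 rounded.
- 2 × 365.25 / 769 = 0.9499, which is <1 either way.
- 2 × 365.25 / 730 = 1.0007, which is in 1-3.4 either way.

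So every patient with two bleeds in 731 to 768 days leaves the most favourable category if the value is rounded first.

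**Step 3: sensitivity to how completion is dated.** Both effects described for seven and two bleeds begin at day 731. If treatment completion is taken as the last injection of an exact weekly schedule (an assumption), the last dose within two years falls on day 1 + 7 × 104 = 729. Then 7 × 365.25 / 729 = 3.507 and 2 × 365.25 / 729 = 1.002. Neither value is in the gap, and neither changes category on rounding. The SAP also does not say whether both end dates are counted, which could shift these limits by one day.

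**Step 4: illustrative upper size.** Protocol 1.2.2.3 reports for HAVEN 1 a treated-bleed rate of 2.9 per year with 62.9% of patients at zero, and an all-bleed rate of 5.5 per year with 37.1% at zero. I assumed an observation window of 24 to 30 weeks and solved the negative binomial zero probability, (1 + m/k)^(−k), for k, where m is the expected count in the window. I then carried the rate forward to two years.

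- P(7 bleeds) = 1.9 to 2.1% for treated bleeds; × 200 gives about 4 patients.
- P(7 bleeds) = 3.2 to 3.5% for all bleeds; × 200 gives about 6 to 7 patients.

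This supposes that all 200 patients complete, and that every one of them has an efficacy period of 731 to 751 days.

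**The case against.** The best case against has four parts.

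**The intent is plain.** Limits printed as 3.4 and 3.5 most naturally mean a cut at 3.5, and each patient's bleeds, days and calculated ABR are to be listed, so the table can be rebuilt under any cut. Both points are fair and keep the matter minor. They do not supply a rule, because one-decimal limits also suggest rounding, and Step 2 shows that the two repairs differ.

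**The <1 limit is not defective.** This stands. A reader might infer that the <1 category is itself ambiguous, or that the SAP misclassifies patients with two bleeds. The text does not support that: the formula is unrounded, and 0.951 to 0.999 is below 1. The shift arises only if someone rounds in order to close the gap.

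**Completers may not reach the gap.** A reader might apply the ±30-day window of the two-year visit (Protocol Appendix 1) to the efficacy period and conclude that many completers must be affected. SAP 4.1 ends the period at completion of treatment, and does not equate that with the visit date. Under the dating in Step 3, on-schedule completers show neither effect. This stands, and it puts the lower bound for completers near zero. Early withdrawals and up-titrated patients could still land in the gap.

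**The illustration leans high.** It ignores discontinuation and up-titration, and it extrapolates a constant rate from 35 patients previously treated on demand to a population that also admits prior prophylaxis. This also stands, so the counts are best read as the top of an illustrative range.

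**Conclusion.** The gap is real and is there on the face of the SAP: a continuous, unrounded ratio is classified with non-contiguous limits, so some attainable values have no category. This is a flaw in the category definition; no stated figure is wrong.

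Its size cannot be settled from the documents. For completers it runs from near zero, if treatment completion is dated at or before day 730, to about 4 patients (treated bleeds) or 7 (all bleeds) under the Step 4 assumptions. The effect on <1 is a consequence of one possible repair, and is a reason to choose the other repair.

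The consequence is limited to descriptive secondary tables and figures. The primary safety analysis, the model-based ABR, the mean and median calculated ABR and the bleed-count categories are unaffected. It is worth correcting because the correction is so cheap; it is not a threat to any conclusion.

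**What to change.** In SAP 4.6.1.2, define the categories on the unrounded calculated ABR as <1, 1 to <3.5, 3.5 to 10, >10. Every value then has exactly one category. Seven bleeds in 731 to 751 days falls in 1 to <3.5, and two bleeds in 731 days or more stays in <1. The change is one line in the SAP and needs no new data and no extra programming.

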#### **4.6.1.3 Cause, type and location of bleed**

Cause of bleed (spontaneous, traumatic, procedure/surgery) and location of bleed by bleed type (Joint, Muscle, other) will be summarized. The analysis will be performed separately for treated bleeds (with 72-hour rule) and all bleeds without applying the 72-Hour rule and including bleeds due to surgeries/procedures.

#### **4.6.1.4 Type of trauma**

Type of trauma will be summarized according to the categories on the eCRF. The traumas are analyzed separately for bleed related trauma and non-bleed related trauma including all trauma. Non-bleed related trauma are identified through bleed number=ND on the trauma form.

#### **4.6.1.5 Time of bleed**

Time of bleed will be summarized by calculating the difference between start time of bleed and start of efficacy period. The time of bleed will be presented as continuous and categorical (1-4 weeks, >4-12 weeks, >12-24 weeks, >24-36 weeks, >36-52 weeks, >52-88 weeks, >88-104 weeks, > 104 weeks).

The analysis will be conducted separately for treated bleeds and all bleeds without applying the 72-Hour rule and including bleeds due to surgeries/procedures.

#### **4.6.1.6 Use of non-emicizumab hemophilia treatments**

The number of treatments to treat a bleed will be summarized. The number of infusions is counted per bleed corresponding to the definition of the primary endpoint, i.e. all treatments that are linked to the same bleed per the 72h rule are considered to belong to the same bleed. If the same treatment/s are associated with multiple bleeds, these are counted multiple times, i.e. linked to both bleeds.

The cumulative dose per kg administered will be summarized by product, e.g. RECOMBINANT FACTOR VIIA [E.G. NOVOSEVEN] or PROTHROMBIN COMPLEX CONCENTRATE [E.G. FEIBA]. The following formulas will be used to annualize the dose and the number of infusions:

$$\frac{\text{Number of Infusions}}{\text{Efficacy Period}} \times 365.25$$

$$\frac{\text{Cumulative dose/kg}}{\text{Efficacy Period}} \times 365.25$$

#### **4.6.1.7 Bleed and Medication Questionnaire Compliance**

Patient compliance to the Bleed and Medication Questionnaire (BMQ) will be analyzed. The compliance will be analyzed separately for entries done via the electronic handheld device only, and for all entries (via electronic handheld device or Site data entry system). A patient will be considered to be compliant if he completes the BMQ at least every 8 days (a filled out BMQ makes the patient compliant for the preceding 7 days, i.e. 8 days in total). The compliance rate will be defined as the number of days covered by a BMQ questionnaire divided by the duration in days of the efficacy period. The BMQ compliance will be summarized in a table and listed. The mean of the compliance rate will also be plotted overtime.

#### **4.6.2 HRQoL (Haem-A-QoL and Haemo-QoL-SF)**

As different HRQoL measures (Haem-A-QoL and the Haemo-QoL-SF) will be used for adult and adolescent patients, all calculations and analyses will be conducted separately for each patient population.

The number and percentage of patients who complete the Haem–A–QoL or Haemo-QoL-SF will be summarized at each scheduled time point. The compliance rate will be plotted over time. The compliance rate is based on the total number of patients expected to complete the questionnaire at a particular time point – i.e., those patients who had the opportunity to complete the scale. The number of expected questionnaires is calculated using the time windows of scheduled visits defined in the protocol. The analysis period used will overlap with the corresponding efficacy period, as the start will be the start of the efficacy period and the end will be either then end of the efficacy period or will be extended to the last entry on the device, for the last efficacy period of a subject, if it occurred later.

Total score and domain sub-scales at each visit for the Haem-A-QoL and Haemo-QoL-SF will be calculated and summarized descriptively. The corresponding mean along with its 95%CI plots will be provided.

The change from baseline to 6 months as well as for each of the post-baseline time points in the total score for each questionnaire will be analyzed by the paired t-test.

The proportion of patients who report changes that exceed clinically meaningful thresholds will be reported. A clinically meaningful threshold is defined as a decrease of 7 points in the Haem-A-QoL total score (Wyrwich et al., 2015), 5 points in the Haemo-QoL-SF total score (Santagostino et al., 2014) and 10 points for physical health.

A descriptive summary of each of the scale will be produced, in which the domain score at each visit and the associated change from baseline will be summarized. Paired t-tests will be performed on the change from baseline to 6months for the scales.

Note: before calculation the scale and total score, several items need to be reverse scored. The reverse scoring for those items is as follows: (1=5), (2=4), (3=3), (4=2), and (5=1). Any (0) will be recoded as missing data for the purposes of scale scoring. For details see Appendix 3: HRQoL QUESTIONNAIRES

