**Table 3** Intra-Patient Comparison of Annualized Bleed Rate with Emicizumab Prophylaxis versus Previous Bypassing Agent Prophylaxis

Endpoint	Emicizumab Prophylaxis (N = 24)	Previous Bypassing Agent Prophylaxis (N = 24)
Treated Bleeds		
ABR (95% CI) [a]	3.3 (1.3, 8.1)	15.7 (11.1, 22.3)
% reduction (95% CI)	79% (51.4%, 91.1%)	
p-value	0.0003	
% patients with 0 bleeds (95% CI)	70.8 (48.9, 87.4)	12.5 (2.7, 32.4)
Median ABR (IQR)	0 (0, 2.2)	12 (5.7, 24.2)

ABR = annualized bleed rate; CI = confidence interval; IQR = interquartile range, 25th percentile to 75th percentile

a. Based on negative binomial regression.

The study evaluated patient-reported hemophilia-related symptoms (painful swellings and presence of joint pain) and physical functioning (pain with movement and difficulty walking far) using the Physical Health Score of the Haemophilia Adult Quality of Life Questionnaire (Haem-A-QoL) for patients aged  $\geq 18$  years. The weekly emicizumab prophylaxis arm (Arm A) showed an improvement compared with the no prophylaxis arm (Arm B) in the Haem-A-QoL Physical Health Subscale score at the Week 25 assessment (Table 3). The improvement in the Physical Health Score was further supported by the Total Score as measured by the Haem-A-QoL at Week 25.

**Table 4** Change in Haem-A-QoL Physical Health Score in Patients (≥ 18 Years of Age) with No Prophylaxis versus Emicizumab Prophylaxis at Week 25

Haem-A-QoL Scores at week 25	Emicizumab Prophylaxis (N = 25 [a])	No Prophylaxis (N = 14 [a])
Physical Health Score (Score range 0 to 100) [b]		
Adjusted mean [c]	32.6	54.2
Difference in adjusted means (95% CI)	21.6 (7.9, 35.2)	
p-value	0.0029	

- a. Number of patients ≥ 18 years who completed the Haem-A-QoL questionnaire.  
b. Lower scores are reflective of better functioning.  
c. Adjusted for baseline, and baseline by treatment group interaction.

The HAVEN 2 study (BH29992; NCT02795767) was a single-arm, multicenter, open-label, clinical study in pediatric males (age < 12 years, or 12–17 years who weigh < 40 kg) with hemophilia A with FVIII inhibitors. Patients received emicizumab prophylaxis at 3 mg/kg once weekly for the first 4 weeks followed by 1.5 mg/kg once weekly thereafter.

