## 6.5 EFFICACY ANALYSES

The efficacy analyses will involve evaluating the number of bleeds over time, the HRQoL of patients, the health status of patients according to EQ-5D-5L scores, and assessing patient preference for the emicizumab regimen compared with the previous regimen used.

The definition of a bleed is described in [Section 4.5.7.1](#). *Patients will be asked to record any hemophilia medication use (including emicizumab) and information regarding any bleeding events.* The patients should record this information at least every week even if they do not experience a bleed. The number of bleeds will be compared with patients' bleed rate prior to study entry and will be summarized descriptively.

HRQoL (using the Haem-A-QoL or the Haemo-QoL-SF), health status (using the EQ-5D-5L), and patient treatment preference will be assessed as per the Schedule of Activities ([Appendix 1](#))

Schedule of Activities

).

Adherence with the HRQoL, health status, and patient treatment preference measures will be summarized.

As different HRQoL measures (Haem-A-QoL and the Haemo-QoL-SF) will be used for adult and adolescent patients, all calculations and analyses will be conducted separately for each patient population. Scale scores for the Haem-A-QoL and Haemo-QoL-SF will be calculated and summarized descriptively. The HRQoL scale scores for all patients will be evaluated after 6 months of treatment, a timepoint which is consistent with other recent registrational studies in hemophilia ([Lentz et al. 2013](#); [Mahlangu et al. 2014](#); [Powell et al. 2013](#)) and analyses of this type of data ([Santagostino et al. 2014](#); [Wyrwich et al. 2015](#)). Paired t-tests will be used to compare the on-treatment scores with the baseline scale scores for each HRQoL measure. Within-patient changes from baseline for the different HRQoL scale scores will also be calculated for each of the on-treatment timepoints. The proportion of patients who report changes that exceed clinically meaningful thresholds will be reported.

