## **4.6 EFFICACY ANALYSIS**

This is a single arm study and, consequently, no formal treatment group comparisons will be conducted.

The efficacy analyses will be based on the ITT population. Efficacy analyses will be restricted to the period before up-titration, if any, except if stated otherwise.

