#### **4.6.3 EQ-5D-5L**

The EQ-5D-5L Questionnaire is a health utility measure to assess patients' health status using 5 dimensions. All five dimensions can be combined in a five-digit number which then describes the patient's health state. This descriptive number is converted to a single summary index utility score by using published weights; in this study we use the UK crosswalk value set (as published by the EuroQol Research Foundation at <http://www.euroqol.org/about-eq-5d/valuation-of-eq-5d>).

Additionally, in the second part of the questionnaire, the current health status is measured by the visual analog scale VAS with values ranging from 0 to 100.

The number and percentage of patients who complete the EQ-5D-5L will be summarized at each scheduled time point. The compliance rate (see section 4.6.2) will be plotted over time. For each of the EQ-5D-5L assessments over time, the number and percentage of patients in each of the five categories for each question will be evaluated. A summary of the EQ-5D-5L index utility score at each visit and the associated change from baseline will

also be provided. The summary statistics presented will include the mean, standard deviation, median, minimum, maximum and interquartile range. Corresponding mean (+95% CI) plots are provided.

In addition, summary statistics including mean, standard deviation, median, minimum, and maximum will be calculated according to the patients' health state using the EuroQoL visual analogue scale (EQ-VAS).

The change from baseline to Post-baseline will be analyzed using the paired t-test. The same outputs will be produced for the EQ-5D-5L VAS score.

The proportion of patients who report changes that exceed the clinically meaningful threshold on the EQ-5D-5L index and the EQ-VAS scores will be reported. A clinically meaningful improvement threshold is defined as a change of +0.07 points in the index utility score and +7 points in the VAS score.

For all completed assessments the five dimensions, the index utility score and VAS score is displayed in a separate listing.

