## APPENDIX 3: HRQOL QUESTIONNAIRES

### Recoding and Scales

Before calculating the scale and total scores several items need to be reverse scored (Table\_App3.01, Table\_App3.02). The reverse scoring for those items is as follows: (1=5), (2=4), (3=3), (4=2), and (5=1). Any (0) will be recoded as missing data for the purposes of scale scoring. In listings of frequencies, the number of patients reporting 'Not applicable' can also be displayed.

After the recoding the 3 scores can be calculated as follows:

1. **Raw Scale Score:** Derived as the sum of all items in a scale. , e.g. the raw score for physical health is the sum of the 5 items from this scale. A Total score is calculated by summing up all of the raw and reverse coded items in the available scales.
2. **Standardized Scale Score:** The raw scale score is divided by the number of items in the scale. That way a comparison of scores across scales per patient is possible.
3. **Transformed Scale Score:** The scores for each scale can be standardized onto a 100 point scale. This is done with the following formula:

$$TSC = 100 \times \frac{(\text{raw scale score} - \text{minimal possible raw score})}{\text{possible range of raw scale scores}}$$
$$= 100 \times \frac{(\text{standardized scale score} - 1)}{4}$$

The transformed Scale Score will be used for all analyses and referred as domain score or total score on the outputs.

Table\_App3.01: The questions from Haem-A-QoL whose items need recoding are:

Category	Question
View of yourself	I felt comfortable with my body
	I was able not to think all the time about my hemophilia
Dealing with hemophilia	I tried to recognize early on when a bleed developed
	I was able to tell whether or not I was bleeding
	I was able to control my bleeds
Treatment	I was satisfied with the hemophilia center
Future	I have been expecting that things will get better in the future
Sports and leisure	I played sports just as much as others

Work and school	I was able to go to work/school regularly in spite of my hemophilia
	I was able to work/study like healthy colleagues

Table\_App3.02: The questions from Haemo-QoL-SF whose items need recoding are:

Category	Question
View of yourself	I felt as well as other boys my age
	I felt contented about my body
Friends	My best friend cared about how I was feeling
	There was a best friend that I felt very close to
	My friends took care of me when I felt bad
Sports and school	I did as much sports as any other kid

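### The HRQoL and EQ-5D-5L responder proportions count meaningful improvement but never meaningful worsening, so in a single-arm trial they have no reference value

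*SAP*

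**What the plan says.** Protocol 6.5 commits to a responder summary for the hemophilia-specific questionnaires: "The proportion of patients who report changes that exceed clinically meaningful thresholds will be reported". It gives no threshold and no direction, and makes a matching commitment for the EQ-5D-5L index and VAS.

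SAP 4.6.2 repeats the commitment and then supplies the thresholds in one sentence: "A clinically meaningful threshold is defined as a decrease of 7 points in the Haem-A-QoL total score", then "5 points in the Haemo-QoL-SF total score" "and 10 points for physical health". The word for decrease governs all three. On these scales a decrease is an improvement; Protocol 1.2.2.3 notes of the physical health score that "Lower scores are reflective of better functioning". SAP 4.6.3 labels its rule as improvement outright: "A clinically meaningful improvement threshold is defined as a change of +0.07 points in the index utility score", and +7 on the VAS.

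Neither SAP section defines a worsening threshold or an unchanged category. Neither names the visits at which the responder proportion is reported, or a confidence interval for it. On comparison, SAP 4.6 states: "This is a single arm study and, consequently, no formal treatment group comparisons will be conducted".

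**The concern.** A proportion of patients who improve by a fixed amount needs something to be read against. In a randomized trial that is the other arm. Here there is none, and questionnaire scores move in both directions from visit to visit without any treatment effect. The natural internal reference is the share who move equally far the wrong way, and the SAP does not plan to show it. A responder percentage could then be read as benefit when part or all of it is variation, and a minority with meaningful deterioration could go unseen behind a favourable mean.

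A second, smaller problem is the counting rule. The SAP reports changes that *exceed* a threshold, but defines the threshold as the decrease itself. Where the score can land exactly on the threshold, the two readings count different patients.

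**Working it through.** The plan states no responder rate, no SD of change for any HRQoL score and no HRQoL precision figure, so there is no planned value to reproduce. The check uses the one piece of variability information available.

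**1. Inputs.** Protocol 1.2.2.3, randomized background trial BH29884, Haem-A-QoL physical health at Week 25: adjusted difference 21.6, 95% CI 7.9 to 35.2, p = 0.0029, n = 25 and 14, model with baseline and baseline-by-arm interaction. SAP 4.6.2 and 4.6.3: thresholds. SAP Appendix 3: the transformed score is 100 × (mean item score − 1)/4, and "the raw score for physical health is the sum of the 5 items from this scale".

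**2. Residual SD.** Half-width = (35.2 − 7.9)/2 = 13.65. With 39 patients and four model terms (35 df), SE = 13.65/2.030 = 6.72. Check: 21.6/6.72 gives p = 0.0028, against 0.0029 stated. Residual SD = 6.72/√(1/25 + 1/14) = 6.72/0.334 = 20.1.

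**3. From residual SD to SD of change.** With equal variances and baseline-to-follow-up correlation ρ, SD of change = residual SD × √(2/(1+ρ)). For ρ from 0.8 to 0.3 (assumed) this gives 21.2 to 25.0. A range of 15 to 25 is used below. The lower end allows for the possibility that 20.1 includes varying treatment response.

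**4. Score steps.** Five items scored 1 to 5 have a raw range of 20, so physical health moves in steps of 100/20 = 5 points, and a change of exactly 10 is attainable. The same arithmetic for the 35-item Haemo-QoL-SF total gives steps of 100/140 = 0.714, so 5 points is exactly 7 steps. For the 46-item Haem-A-QoL total with every item answered, the step is 100/184 = 0.543 and 7 points is not a whole number of steps, so the wording makes no difference there.

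**5. Physical health under no effect.** Assume normal change with mean 0. On a 5-point grid, P(improve by ≥ 10) = Φ(−7.5/SD) and P(improve by > 10) = Φ(−12.5/SD). By symmetry the same shares worsen.

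| SD of change | improve ≥ 10 | improve > 10 |
|---|---|---|
| 15 | Φ(−0.500) = 31% | Φ(−0.833) = 20% |
| 20 | Φ(−0.375) = 35% | Φ(−0.625) = 27% |
| 25 | Φ(−0.300) = 38% | Φ(−0.500) = 31% |

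At SD 20, reading *exceed* strictly or not moves 35.4% − 26.6% = about 9% of patients.

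**6. Haem-A-QoL total, 7 points, under no effect.** The SD of change is an assumption throughout. Φ(−7/SD) gives 19% at SD 8, 24% at 10, 28% at 12, 33% at 16 and 36% at 20. No rate is computed for the EQ-5D-5L thresholds, because the documents give no SD for those scores.

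**7. What two-directional reporting would show.** Under no effect, improved and worsened shares are equal and the net is 0. If physical health change instead averaged −21.6 with SD 20.1 (borrowing the between-arm difference as an illustration, and treating the score as continuous), Φ(11.6/20.1) = 72% would improve past 10 points and Φ(−31.6/20.1) = 6% would worsen past it.

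**The case against.** The strongest reply is that the HRQoL section as a whole does not present noise as benefit. Total and domain scores are summarized by visit, mean scores are plotted with 95% CIs, and change from baseline in the total score is tested at every post-baseline time point. Under no effect those results would centre on zero beside the responder figure. HRQoL is also a secondary endpoint in a descriptive safety study, and Protocol 6.5 leaves detail to the SAP, so choosing a direction can be called elaboration. All of this is fair and limits the seriousness. It does not supply the missing row: a mean change does not tell the reader what share of patients deteriorated by a meaningful amount.

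Three stronger readings are tempting, and the documents do not support them:

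- A reader might infer that patients who worsen are removed. Nothing excludes them from the responder denominator or from the other summaries.
- A reader might infer that about a third of patients would be responders under no effect, whatever the score. That figure is approached only for physical health, and only with non-strict counting and an assumed SD. For the 7-point total score, one third would need an SD of about 16, which the documents do not give.
- A reader might accumulate chance responders over the five post-baseline assessments. The SAP plans no responder-at-any-visit analysis, so such a rate would match no planned output.

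The SD of 20.1 is also borrowed. It is a baseline-adjusted residual SD from 39 patients in another trial, partly on treatment, and the normal model ignores the 0–100 limits of the score.

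**Conclusion.** The point holds as a reporting gap. The SAP narrows an undirected protocol commitment to improvement only, and the resulting proportion cannot be interpreted on its own in a trial without a control arm. The size is illustrative. For physical health with zero mean change and SD 15–25, 31–38% would pass as improved with ≥ 10 and 20–31% with > 10, and the same shares would worsen. For the 7-point total score the range is about 19–36% on wholly assumed SDs of 8–20. The counting rule is ambiguous and would move about 9% of patients on physical health at SD 20.

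This is worth correcting but does not touch the primary safety objective. Setting worsening beside improvement deals with symmetric variation only. It cannot remove regression to the mean or the effect of open-label expectation, and the result remains descriptive.

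**What to change.** In SAP 4.6.2 and 4.6.3:

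- Classify each patient with a baseline and a visit score as improved, unchanged or worsened, using the same threshold in both directions (7, 5 and 10 points; 0.07 and 7 for EQ-5D-5L).
- Report all three percentages, with the number assessed, at each scheduled post-baseline visit.
- Report the net difference, improved minus worsened, with a 95% CI for paired proportions. A simple large-sample variance is [p₊ + p₋ − (p₊ − p₋)²]/n, where p₊ and p₋ are the improved and worsened proportions.
- Replace *exceed* with *reach or exceed (≥)*.

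The cost is a few SAP sentences and a few table rows per score, from change scores already being derived; no new data are needed. The drawback for the sponsor is that the responder figure will stand next to a worsening figure. If there is real benefit, the contrast makes it clearer.
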